#### Section B-4.7 Disabling endometriosis associated pain preventing the woman from working or attending social events at study entry

Table B-4.7.1 Disabling endometriosis associated pain preventing the woman from working or attending social events at study entry, ITT population, Complete cohort

	DNG	OAED			NAED			Allocation unknown	Total
		GnRH-a	Danazol	All OAED	CC	Other progestin	All NAED		
Number (%) of women	xx ( 100%)	xx ( 100%)	xx ( 100%)	xx ( 100%)					
Disabling endometriosis associated pain*									
Yes	xx ( xx.x%)	xx ( xx.x%)	xx ( xx.x%)	xx ( xx.x%)					
No	xx ( xx.x%)	xx ( xx.x%)	xx ( xx.x%)	xx ( xx.x%)					
Missing	xx ( xx.x%)	xx ( xx.x%)	xx ( xx.x%)	xx ( xx.x%)					

Note:\* On at least two days in the last four weeks before study entry

Table B-4.7.2	Disabling endometriosis associated pain preventing the woman from working or attending social events at study entry, AT population, Complete cohort
Table B-4.7.3	Disabling endometriosis associated pain preventing the woman from working or attending social events at study entry, AT population, Starter
Table B-4.7.4	Disabling endometriosis associated pain preventing the woman from working or attending social events at study entry, AT population, Switcher
Table B-4.7.5	Disabling endometriosis associated pain preventing the woman from working or attending social events at study entry, AT population, Restarter
Table B-4.7.6 by surge	Disabling endometriosis associated pain preventing the woman from working or attending social events at study entry, AT population, Diagnosis confirmed ry
Table B-4.7.7 clinical sy	Disabling endometriosis associated pain preventing the woman from working or attending social events at study entry, AT population, Diagnosis based on mptoms
Table B-4.7.8	Disabling endometriosis associated pain preventing the woman from working or attending social events at study entry, AT population, Germany
Table B-4.7.9	Disabling endometriosis associated pain preventing the woman from working or attending social events at study entry, AT population, Poland
Table B-4.7.10	Disabling endometriosis associated pain preventing the woman from working or attending social events at study entry, AT population, Hungary
Table B-4.7.11	Disabling endometriosis associated pain preventing the woman from working or attending social events at study entry, AT population, Switzerland
Table B-4.7.12	Disabling endometriosis associated pain preventing the woman from working or attending social events at study entry, AT population, Russia

Supporting document SOP BMT 01.09 – Doc 5002.02 – Effective date 21.03.2017

#### Section B-4.8 Severity of endometriosis associated pain at study entry

Table B-4.8.1 Severity of endometriosis associated pain at study entry, ITT population, Complete cohort

	DNG	OAED		NAED			Allocation unknown	Total	
		GnRH-a	Danazol	All OAED	CC	Other progestin	All NAED		
Number (%) of women	xx ( 100%)	xx ( 100%)	xx ( 100%)	xx ( 100%)					
Pain severity score*									
Mild (0-3)	xx ( xx.x%)	xx ( xx.x%)	xx ( xx.x%)	xx ( xx.x%)					
Moderate (4-7)	xx ( xx.x%)	xx ( xx.x%)	xx ( xx.x%)	xx ( xx.x%)					
Severe (8-10)	xx ( xx.x%)	xx ( xx.x%)	xx ( xx.x%)	xx ( xx.x%)					
Missing	xx ( xx.x%)	xx ( xx.x%)	xx ( xx.x%)	xx ( xx.x%)					

Note: \*Pain severity score is defined from 0 (no pain) up to 10 (unbearable pain).

Table B-4.8.2	Severity of endometriosis associated pain at study entry, AT population, Complete cohort
Table B-4.8.3	Severity of endometriosis associated pain at study entry, AT population, Starter
Table B-4.8.4	Severity of endometriosis associated pain at study entry, AT population, Switcher
Table B-4.8.5	Severity of endometriosis associated pain at study entry, AT population, Restarter
Table B-4.8.6	Severity of endometriosis associated pain at study entry, AT population, Diagnosis confirmed by surgery
Table B-4.8.7	Severity of endometriosis associated pain at study entry, AT population, Diagnosis based on clinical symptoms
Table B-4.8.8	Severity of endometriosis associated pain at study entry, AT population, Germany
Table B-4.8.9	Severity of endometriosis associated pain at study entry, AT population, Poland
Table B-4.8.10	Severity of endometriosis associated pain at study entry, AT population, Hungary
Table B-4.8.11	Severity of endometriosis associated pain at study entry, AT population, Switzerland
Table B-4.8.12	Severity of endometriosis associated pain at study entry, AT population, Russia
Table B-4.8.13	Severity of endometriosis associated pain at study entry, AT population, Ukraine

Supporting document SOP BMT 01.09 - Doc 5002.02 - Effective date 21.03.2017

#### Section B-5 Medical history

Section B-5.1 Self-reported history of selected risk factors at study entry

Table B-5.1.1 Self-reported history of selected risk factors at study entry, ITT population, Complete cohort

	DNG	OAED			NAED			Allocation unknown	Total
		GnRH-a	Danazol	All OAED	CC	Other progestin	All NAED		
Number (%) of women	xx ( 100%)	xx ( 100%)	xx ( 100%)	xx ( 100%)					
Endometriosis of relatives*	xx ( xx.x%)	xx ( xx.x%)	xx ( xx.x%)	xx ( xx.x%)					
Depression of relatives*	xx ( xx.x%)	xx ( xx.x%)	xx ( xx.x%)	xx ( xx.x%)					
Thrombosis or pulmonary embolism of relatives*	xx ( xx.x%)	xx ( xx.x%)	xx ( xx.x%)	xx ( xx.x%)					
BMI >= 25.0 to <30.0	xx ( xx.x%)	xx ( xx.x%)	xx ( xx.x%)	xx ( xx.x%)					
BMI >=30.0 to <35.0	xx ( xx.x%)	xx ( xx.x%)	xx ( xx.x%)	xx ( xx.x%)					
BMI >= 35.0	xx ( xx.x%)	xx ( xx.x%)	xx ( xx.x%)	xx ( xx.x%)					
Smoker	xx ( xx.x%)	xx ( xx.x%)	xx ( xx.x%)	xx ( xx.x%)					
Heavy smoker (>15 cigarettes / day)	xx ( xx.x%)	xx ( xx.x%)	xx ( xx.x%)	xx ( xx.x%)					

Note: \* First-degree relatives only.

Table B-5.1.2	Self-reported history of selected risk factors at study entry, AT population, Complete cohort
Table B-5.1.3	Self-reported history of selected risk factors at study entry, AT population, Starter
Table B-5.1.4	Self-reported history of selected risk factors at study entry, AT population, Switcher
Table B-5.1.5	Self-reported history of selected risk factors at study entry, AT population, Restarter
Table B-5.1.6	Self-reported history of selected risk factors at study entry, AT population, Diagnosis confirmed by surgery
Table B-5.1.7	Self-reported history of selected risk factors at study entry, AT population, Diagnosis based on clinical symptoms
Table B-5.1.8	Self-reported history of selected risk factors at study entry, AT population, Germany
Table B-5.1.9	Self-reported history of selected risk factors at study entry, AT population, Poland
Table B-5.1.10	Self-reported history of selected risk factors at study entry, AT population, Hungary
Table B-5.1.11	Self-reported history of selected risk factors at study entry, AT population, Switzerland
Table B-5.1.12	Self-reported history of selected risk factors at study entry, AT population, Russia
Table B-5.1.13	Self-reported history of selected risk factors at study entry, AT population, Ukraine

Supporting document SOP BMT 01.09 – Doc 5002.02 – Effective date 21.03.2017

#### Section B-5.2 Self-reported history of selected diseases at study entry

Table B-5.2.1 Self-reported history of selected diseases at study entry, ITT population, Complete cohort

	DNG	OAED			NAED			Allocation unknown	Total
		GnRH-a	Danazol	All OAED	CC	Other progestin	All NAED		
Number (%) of women	xx ( 100%)	xx ( 100%)	xx ( 100%)	xx ( 100%)					
Depression*	xx ( xx.x%)	xx ( xx.x%)	xx ( xx.x%)	xx ( xx.x%)					
Anemia*	xx ( xx.x%)	xx ( xx.x%)	xx ( xx.x%)	xx ( xx.x%)					
Myocardial infarction*	xx ( xx.x%)	xx ( xx.x%)	xx ( xx.x%)	xx ( xx.x%)					
Stroke*	xx ( xx.x%)	xx ( xx.x%)	xx ( xx.x%)	xx ( xx.x%)					
Clotting lung (pulmonary embolism) *	xx ( xx.x%)	xx ( xx.x%)	xx ( xx.x%)	xx ( xx.x%)					
Deep venous thrombosis*	xx ( xx.x%)	xx ( xx.x%)	xx ( xx.x%)	xx ( xx.x%)					
Cancer*	xx ( xx.x%)	xx ( xx.x%)	xx ( xx.x%)	xx ( xx.x%)					
Other serious diseases*	xx ( xx.x%)	xx ( xx.x%)	xx ( xx.x%)	xx ( xx.x%)					
Any none endometriosis related surgery	xx ( xx.x%)	xx ( xx.x%)	xx ( xx.x%)	xx ( xx.x%)					

Note: \* Treated by HCP only

Self-reported history of selected diseases at study entry, AT population, Complete cohort
Self-reported history of selected diseases at study entry, AT population, Starter
Self-reported history of selected diseases at study entry, AT population, Switcher
Self-reported history of selected diseases at study entry, AT population, Restarter
Self-reported history of selected diseases at study entry, AT population, Diagnosis confirmed by surgery
Self-reported history of selected diseases at study entry, AT population, Diagnosis based on clinical symptoms
Self-reported history of selected diseases at study entry, AT population, Germany
Self-reported history of selected diseases at study entry, AT population, Poland
Self-reported history of selected diseases at study entry, AT population, Hungary
Self-reported history of selected diseases at study entry, AT population, Switzerland
Self-reported history of selected diseases at study entry, AT population, Russia
Self-reported history of selected diseases at study entry, AT population, Ukraine

Supporting document SOP BMT 01.09 - Doc 5002.02 - Effective date 21.03.2017

#### Section B-6 Medication and other procedures for endometriosis treatment

Section B-6.1 Medication prescribed for the treatment of endometriosis during the past two years before study entry

Table B-6.1.1 Medication prescribed for the treatment of endometriosis during the past two years before study entry, ITT population, Complete cohort

	DNG	OAED			NAED			Allocation unknown	Total
		GnRH-a	Danazol	All OAED	CC	Other progestin	All NAED		
Number (%) of women	xx ( 100%)	xx ( 100%)	xx ( 100%)	xx ( 100%)					
Endometriosis medication									
Thereof*									
Category 1	xx ( xx.x%)	xx ( xx.x%)	xx ( xx.x%)	xx ( xx.x%)					
Category 2	xx ( xx.x%)	xx ( xx.x%)	xx ( xx.x%)	xx ( xx.x%)					
Category 3	xx ( xx.x%)	xx ( xx.x%)	xx ( xx.x%)	xx ( xx.x%)					
Categories <1%	xx ( xx.x%)	xx ( xx.x%)	xx ( xx.x%)	xx ( xx.x%)					
Missing	xx ( xx.x%)	xx ( xx.x%)	xx ( xx.x%)	xx ( xx.x%)					

Note: \* Multiple answers possible

Table B-6.1.2	Medication prescribed for the treatment of endometriosis during the past two years before study entry, AT population, Complete cohort
Table B-6.1.3	Medication prescribed for the treatment of endometriosis during the past two years before study entry, AT population, Starter
Table B-6.1.4	Medication prescribed for the treatment of endometriosis during the past two years before study entry, AT population, Switcher
Table B-6.1.5	Medication prescribed for the treatment of endometriosis during the past two years before study entry, AT population, Restarter
Table B-6.1.6	Medication prescribed for the treatment of endometriosis during the past two years before study entry, AT population, Diagnosis confirmed by surgery
Table B-6.1.7	Medication prescribed for the treatment of endometriosis during the past two years before study entry, AT population, Diagnosis based on clinical
symptom	S
Table B-6.1.8	Medication prescribed for the treatment of endometriosis during the past two years before study entry, AT population, Germany
Table B-6.1.9	Medication prescribed for the treatment of endometriosis during the past two years before study entry, AT population, Poland
Table B-6.1.10	Medication prescribed for the treatment of endometriosis during the past two years before study entry, AT population, Hungary
Table B-6.1.11	Medication prescribed for the treatment of endometriosis during the past two years before study entry, AT population, Switzerland
Table B-6.1.12	Medication prescribed for the treatment of endometriosis during the past two years before study entry, AT population, Russia
Table B-6.1.13	Medication prescribed for the treatment of endometriosis during the past two years before study entry, AT population, Ukraine

Supporting document SOP BMT 01.09 – Doc 5002.02 – Effective date 21.03.2017

#### Section B-6.2 Medication and other procedures for endometriosis treatment at study entry

Table B-6.2.1 Medication and other procedures for endometriosis treatment at study entry, ITT population, Complete cohort

	DNG		OAED		NAED			Allocation unknown	Total
		GnRH-a	Danazol	All OAED	CC	Other progestin	All NAED		
Number (%) of women	xx ( 100%)	xx ( 100%)	xx ( 100%)	xx ( 100%)					
Other measures taken for treatment of endometriosis Thereof*	xx ( xx.x%)	xx ( xx.x%)	xx ( xx.x%)	xx ( xx.x%)					
Non-prescription pain killers	xx ( xx.x%)	xx ( xx.x%)	xx ( xx.x%)	xx ( xx.x%					
Natural/herbal products	xx ( xx.x%)	xx ( xx.x%)	xx ( xx.x%)	xx ( xx.x%					
Acupuncture	xx ( xx.x%)	xx ( xx.x%)	xx ( xx.x%)	xx ( xx.x%					
Dietary modification	xx ( xx.x%)	xx ( xx.x%)	xx ( xx.x%)	xx ( xx.x%)					
Massage/manual therapy	xx ( xx.x%)	xx ( xx.x%)	xx ( xx.x%)	xx ( xx.x%)					
Home remedies	xx ( xx.x%)	xx ( xx.x%)	xx ( xx.x%)	xx ( xx.x%)					
Other	xx ( xx.x%)	xx ( xx.x%)	xx ( xx.x%)	xx ( xx.x%)					
Nothing else	xx ( xx.x%)	xx ( xx.x%)	xx ( xx.x%)	xx ( xx.x%)					
Missing	xx ( xx.x%)	xx ( xx.x%)	xx ( xx.x%)	xx ( xx.x%)					

Note: \* Multiple answers possible

Table B-6.2.2	Medication and other procedures for endometriosis treatment at study entry, AT population, Complete cohort
Table B-6.2.3	Medication and other procedures for endometriosis treatment at study entry, AT population, Starter
Table B-6.2.4	Medication and other procedures for endometriosis treatment at study entry, AT population, Switcher
Table B-6.2.5	Medication and other procedures for endometriosis treatment at study entry, AT population, Restarter
Table B-6.2.6	Medication and other procedures for endometriosis treatment at study entry, AT population, Diagnosis confirmed by surgery
Table B-6.2.7	Medication and other procedures for endometriosis treatment at study entry, AT population, Diagnosis based on clinical symptoms
Table B-6.2.8	Medication and other procedures for endometriosis treatment at study entry, AT population, Germany
Table B-6.2.9	Medication and other procedures for endometriosis treatment at study entry, AT population, Poland
Table B-6.2.10	Medication and other procedures for endometriosis treatment at study entry, AT population, Hungary
Table B-6.2.11	Medication and other procedures for endometriosis treatment at study entry, AT population, Switzerland
Table B-6.2.12	Medication and other procedures for endometriosis treatment at study entry, AT population, Russia
Table B-6.2.13	Medication and other procedures for endometriosis treatment at study entry, AT population, Ukraine

Supporting document SOP BMT 01.09 – Doc 5002.02 – Effective date 21.03.2017

#### Section B-6.3 Regular use of other than endometriosis treatment medication at study entry

Table B-6.3.1 Regular use of other than endometriosis treatment medication at study entry, ITT population, Complete cohort

	DNG	OAED			NAED			Allocation unknown	Total
		GnRH-a	Danazol	All OAED	CC	Other progestin	All NAED		
Number (%) of women	xx ( 100%)	xx ( 100%)	xx ( 100%)	xx ( 100%					
Regular use of medication									
Any	xx ( xx.x%)	xx ( xx.x%)	xx ( xx.x%)	xx ( xx.x%					
Thereof*									
Category 1	xx ( xx.x%)	xx ( xx.x%)	xx ( xx.x%)	xx ( xx.x%					
Category 2	xx ( xx.x%)	xx ( xx.x%)	xx ( xx.x%)	xx ( xx.x%)					
Category 3	xx ( xx.x%)	xx ( xx.x%)	xx ( xx.x%)	xx ( xx.x%					
Categories <1%	xx ( xx.x%)	xx ( xx.x%)	xx ( xx.x%)	xx ( xx.x%					
Missing	xx ( xx.x%)	xx ( xx.x%)	xx ( xx.x%)	xx ( xx.x%					

Note: \*ATC (version: 2010), 1st level. Women may appear in more than one category.

Table B-6.3.2	Regular use of other than endometriosis treatment medication at study entry, AT population, Complete cohort
Table B-6.3.3	Regular use of other than endometriosis treatment medication at study entry, AT population, Starter
Table B-6.3.4	Regular use of other than endometriosis treatment medication at study entry, AT population, Switcher
Table B-6.3.5	Regular use of other than endometriosis treatment medication at study entry, AT population, Restarter
Table B-6.3.6	Regular use of other than endometriosis treatment medication at study entry, AT population, Diagnosis confirmed by surgery
Table B-6.3.7	Regular use of other than endometriosis treatment medication at study entry, AT population, Diagnosis based on clinical symptoms
Table B-6.3.8	Regular use of other than endometriosis treatment medication at study entry, AT population, Germany
Table B-6.3.9	Regular use of other than endometriosis treatment medication at study entry, AT population, Poland
Table B-6.3.10	Regular use of other than endometriosis treatment medication at study entry, AT population, Hungary
Table B-6.3.11	Regular use of other than endometriosis treatment medication at study entry, AT population, Switzerland
Table B-6.3.12	Regular use of other than endometriosis treatment medication at study entry, AT population, Russia
Table B-6.3.13	Regular use of other than endometriosis treatment medication at study entry, AT population, Ukraine

Supporting document SOP BMT 01.09 – Doc 5002.02 – Effective date 21.03.2017

#### Section B-6.4 Psychotropic medication at study entry

Table B-6.4.1 Psychotropic medication at study entry, ITT population, Complete cohort

	DNG	OAED		NAED			Allocation unknown	Total	
		GnRH-a	Danazol	All OAED	CC	Other progestin	All NAED		
Number (%) of women	xx ( 100%)	xx ( 100%)	xx ( 100%)	xx ( 100%					
Psychotropic medication									
Category 1	xx ( xx.x%)	xx ( xx.x%)	xx ( xx.x%)	xx ( xx.x%					
Category 2	xx ( xx.x%)	xx ( xx.x%)	xx ( xx.x%)	xx ( xx.x%					
Category 3	xx ( xx.x%)	xx ( xx.x%)	xx ( xx.x%)	xx ( xx.x%					
 Categories <1%	xx ( xx.x%)	xx ( xx.x%)	xx ( xx.x%)	xx ( xx.x%					
Missing	xx ( xx.x%)	xx ( xx.x%)	xx ( xx.x%)	xx ( xx.x%					

Note: \*ATC (version: 2010), 3rd level. Women may appear in more than one category.

Table B-6.4.2	Psychotropic medication at study entry, AT population, Complete cohort
Table B-6.4.3	Psychotropic medication at study entry, AT population, Starter
Table B-6.4.4	Psychotropic medication at study entry, AT population, Switcher
Table B-6.4.5	Psychotropic medication at study entry, AT population, Restarter
Table B-6.4.6	Psychotropic medication at study entry, AT population, Diagnosis confirmed by surgery
Table B-6.4.7	Psychotropic medication at study entry, AT population, Diagnosis based on clinical symptoms
Table B-6.4.8	Psychotropic medication at study entry, AT population, Germany
Table B-6.4.9	Psychotropic medication at study entry, AT population, Poland
Table B-6.4.10	Psychotropic medication at study entry, AT population, Hungary
Table B-6.4.11	Psychotropic medication at study entry, AT population, Switzerland
Table B-6.4.12	Psychotropic medication at study entry, AT population, Russia
Table B-6.4.13	Psychotropic medication at study entry, AT population, Ukraine

Supporting document SOP BMT 01.09 – Doc 5002.02 – Effective date 21.03.2017

#### Section B-7 Distribution and selected baseline characteristics of Visanne long-term user

#### Section B-7.1 Duration of Visanne use

Table B-7.1.1 Duration of Visanne use

	DNG long-term user*
Number (%) of women	xx ( 100%)
Duration of DNG use	
15 months to < 24 months	xx ( xx.x%)
24 months to < 30 months	xx ( xx.x%)
30 months to < 36 months	xx ( xx.x%)
36 months to < 42 months	xx ( xx.x%)
42 months to < 48 months	xx ( xx.x%)
48 months to < 54 months	xx ( xx.x%)
54 months to < 60 months	xx ( xx.x%)
60 months to < 66 months	xx ( xx.x%)
66 months to < 72 months	xx ( xx.x%)
72 months to < 78 months	xx ( xx.x%)
78 months to < 84 months	xx ( xx.x%)
84 months and more	xx ( xx.x%)

Note: \*Long-term: defined as continuous use for >= 15 months. They may have started with other than DNG treatment.

Table B-7.1.2	Duration of Visanne use, Starter
Table B-7.1.3	Duration of Visanne use, Switcher
Table B-7.1.4	Duration of Visanne use, Restarter
Table B-7.1.5	Duration of Visanne use, Diagnosis confirmed by surgery
Table B-7.1.6	Duration of Visanne use, Diagnosis based on clinical symptoms
Table B-7.1.7	Duration of Visanne use, Germany
Table B-7.1.8	Duration of Visanne use, Poland
Table B-7.1.9	Duration of Visanne use, Hungary
Table B-7.1.10	Duration of Visanne use, Switzerland
Table B-7.1.11	Duration of Visanne use, Russia
Table B-7.1.12	Duration of Visanne use. Ukraine

Supporting document SOP BMT 01.09 – Doc 5002.02 – Effective date 21.03.2017

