#### Secondary objectives are:

- To characterize the baseline risk of users of the individual formulations (lifetime history of co-morbidity, risk markers, co-medication, socio-demographic and lifestyle data).
- To analyze the drug utilization pattern of DNG and other endometriosis treatments in a study population that is representative for typical use of the individual preparations under routine medical conditions.
- To investigate the risks of short and long-term use of DNG and of established endometriosis treatments in adolescent women.

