#### 3. Study Design

This is a large, prospective, controlled, non-interventional, long-term cohort study which follows two cohorts, users of DNG and users of other medications used for the treatment of endometriosis. The cohorts consist of new users (starter and restarter) or switcher of a hormonal endometriosis treatment. A "non-interference" approach will be used to provide standardized, comprehensive, reliable information on endometriosis treatment patterns.

A follow-up assessment for each woman is scheduled 6, 12, 24, 36 and depending on the date of enrollment 48, 60, 72 and 84 months after baseline. Women will be followed-up for at least 2 years. Women recruited in the early phase of the study will be followed-up until study endpoint [max. 7 years]. By means of these contacts, almost all relevant clinical outcomes will be captured.

However, during the first year of the study, less than 15% of the planned recruitment target within that time frame was achieved (i.e. 1,191 women were recruited rather than the anticipated 8,334 women). As a consequence, the overall recruitment phase was longer (and therefore the observation time was less) than we had expected. In order to achieve the envisaged total observation time of 84,000 women years, the follow-up period will be prolonged by one year (until end of QII 2018).

All clinically relevant serious adverse events will be verified by ZEG through contact with the relevant physicians and by reviewing pertinent source documentation. A standard algorithm will be used to classify 'clinically relevant depression' and 'medically treated anemia' as 'confirmed' or 'not confirmed'. At the end of the study, this classification will be verified by blinded independent adjudication

treatment with GnRH, an estrogen and/or a progestogen (add-back therapy) will be considered as a single treatment regimen. In cases where add-back therapy is used the predefined end-point is the cessation of the add-back therapy.

 Users of non-approved hormonal medications prescribed for endometriosis treatment are additionally followed up and included in the analysis.

 First ever user of EMT

 EMT use after intake break (>= 4 weeks)

 Switching from another EMT

 According Study Protocol, Amendment of September 30, 2017

Supporting document SOP BMT 01.09 - Doc 5002.02 - Effective date 21.03.2017

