#### 3.1 Study population, inclusion and exclusion criteria

It was planned to implement the study in several European countries including, but not necessarily limited to, Germany, Austria, France, and Poland. However, the study was initiated in Germany in 2010, and in Hungary and Poland in early 2011. Because of recruitment problems, additional countries were included to broaden the recruitment base: Ukraine, Russia, and Switzerland started recruitment in 2012.

Recruitment of the cohort members will be conducted via a network of approximately 1,000 physicians (study centers) managing women with a diagnosis of endometriosis. The combined cohort will include 25,000 women .

At the participating centers, all women prescribed a new treatment for endometriosis are to be asked by their physician if they are willing to participate. The physician is to explain the nature of the study, its purpose and associated procedures, and the expected duration of follow-up for each woman prior to her study entry. Each woman is to have ample opportunity to ask questions and must be informed about her right to withdraw from the study at any time without disadvantage and without having to provide reasons for her decision. This information will be provided on an informed consent and data privacy form which must be signed by all study participants. These documents are to be approved by the relevant local Ethics Committees and the relevant Data Privacy Office, if applicable.

Once enrolled, a subject may discontinue use of the relevant medication at any time. However, subjects will continue to be followed whether or not they remain on their treatment for endometriosis, provided that they do not withdraw their consent. During the follow-up phase, subjects will be asked whether they have discontinued their treatment or whether they have switched to another medication or received surgical treatment to manage their endometriosis. Information on the date and reason for discontinuation or switching during the follow-up phase will also be collected.

The study participants are women who

- are users of a newly prescribed regimen for endometriosis (starter, switcher or restarter)
- are willing to participate in this long-term follow-up study.

There are no specific medical inclusion or exclusion criteria. However, women

- who are not cooperative/available for follow-up may be excluded from study participation

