#### 3.2 Study Flow Chart

Recruitment: 6 European countries (Germany, Poland, Russia, Hungary, Switzerland, Ukraine)

Indication: Starter, restarter and switcher initiating a new treatment for endometriosis and

willing to participate

Recruitment time: approx. 58 months (end of 2010 – June 2014; spring 2015 – June 2016)

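### Tables B-7.1.1 to B-7.1.12 do not separate ended from still-running Visanne use, so shares beyond 48 months understate duration of use and are not comparable between countries

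*SAP*

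**What the plan says.** The mock table "Table B-7.1.1 Duration of Visanne use" puts DNG long-term users into 12 duration rows, from 15 to under 24 months up to "84 months and more", as counts and percentages. It is repeated for three user types, two diagnosis classes and six countries. The footnote describes the population as "defined as continuous use for >= 15 months. They may have started with other than DNG treatment". There is no row or column for ongoing use, no rule for drop-out or loss to follow-up, and no number at risk.

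The calendar comes from other parts of the SAP:
- Section 3.2: "Recruitment time: approx. 58 months (end of 2010 – June 2014; spring 2015 – June 2016". A footnote in section 3.1 says the restart was recommended for 2,000 women on other approved medications (OAED).
- Section 3: follow-up runs to the end of QII 2018, with a maximum of 7 years and this minimum: "Women will be followed-up for at least 2 years".
- Section 3.1: Germany opened in 2010, Hungary and Poland in early 2011, and "Ukraine, Russia, and Switzerland started recruitment in 2012".

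The table bears on a secondary objective: "To analyze the drug utilization pattern of DNG and other endometriosis treatments".

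**The concern.** For each woman the table can show only the shorter of two times: how long she used DNG, and how long she was observed using it. A woman who entered in June 2014 and is still taking DNG in June 2018 is filed at 48 months, in the same row as a woman who stopped at 48 months. The upper rows therefore mix persistence with calendar time.

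Two readings would go wrong. The title invites a reader to take the percentages as how long Visanne is used, and for that purpose the long-duration shares can only be too low. The six country tables invite comparison, but the countries do not have the same maximum observable duration. What is at stake is the description of long-term use under the drug-utilization objective.

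**Working it through.** **Calendar check.** December 2010 to June 2014 is 43 months and April 2015 to June 2016 is 15 months. Together they make the stated 58. June 2016 to June 2018 is 24 months, which matches the stated two-year minimum.

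**Maximum observable use for a woman on DNG from entry, to 30 June 2018:**
- Germany, Poland and Hungary: 84 months (calendar time of 86 to 92 months, limited by the 7-year maximum).
- Russia, Ukraine and Switzerland: 78 months if opened in January 2012, 66 months if opened at the end of 2012.
- Anyone entering in June 2014: 48 months.

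So the rows for 78 to under 84 months and for 84 months or more cannot be filled in the three countries opened in 2012. In the main recruitment block every woman has at least 48 months of potential follow-up, so staggered entry alone affects only the rows beyond 48 months.

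**Formulas.** Assume a constant stopping rate h per year and DNG from entry. The true share of long-term users reaching m months is exp(−h(m − 15)/12). Without drop-out, the tabulated share is that value times the fraction of women whose follow-up could reach m months. With 10% annual drop-out it is further multiplied by 0.9^((m − 15)/12).

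**Fraction who could reach 60 months (entry by mid-2013).** Inputs: 1,191 women in the first year (SAP section 3) of 25,000 (section 3.1). Assumed: the first year runs from 2010.95 to 2011.95, and the rest enter uniformly to mid-2014.
- 1,191/25,000 = 0.0476
- 0.0476 + 0.9524 × (1.55/2.55) = 0.63
- With drop-out: 0.63 × 0.9^3.75 = 0.63 × 0.674 = 0.42

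The same calculation gives 0.25 at 72 months and 0.03 at 84 months. These ratios do not depend on h; only the absolute gap does.

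| Stopping rate (assumed) | True share, ≥60 months | Tabulated, no drop-out | Tabulated, 10% drop-out | Censored among long-term users |
|---|---|---|---|---|
| 0.25/year | 39.2% | 24.5% | 16.5% | 37% to 47% |
| 0.5/year | 15.3% | 9.6% | 6.4% | 14% to 25% |
| 0.8/year | 5.0% | 3.1% | 2.1% | 4.5% to 14% |

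The last column runs from no drop-out to 10% drop-out; it and the tabulated shares were checked by simulation.

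**At 48 months.** Without drop-out there is no loss: 50.3% true and 50.3% tabulated at 0.25/year. With drop-out, 50.3% × 0.9^2.75 = 37.6%. That whole gap is drop-out.

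**Countries with identical persistence** (0.25/year, no drop-out, uniform entry from opening to June 2014, true share at ≥60 months 39.2%):
- Germany: 2.58/3.58 × 39.2% = 28.2%
- Poland and Hungary: 2.33/3.33 × 39.2% = 27.4%
- 2012 countries: 1.5/2.5 × 39.2% = 23.5% (January opening), down to 1.0/2.0 × 39.2% = 19.6% (mid-2012 opening)

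The 2012 countries are 17% to 31% below Germany in relative terms, from start dates alone. At 78 months or more the true share is 26.9%; the tables would show about 8.1% in Germany and zero in the 2012 countries.

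**The case against.** The best defence is that B-7.1 is descriptive. It sits among the population characteristics, nothing in the SAP calls its durations complete, and section 5.4.4 defines treatment pattern through discontinuation reasons and the first switch, without mentioning duration. As duration observed in the study, the table is correct.

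Other outputs also bear on stopping. C-2.7 gives discontinuation proportions for long-term users, C-3.4 shows their women-years in all cohorts, C-1.3 and C-2.1 give discontinuation by reason per treatment start, and a Cox model is planned for treatment failure. This limits the point, because the SAP does not rely on B-7.1 alone. None of these outputs corrects the duration rows, however, and the table's title does not say that duration is only as observed.

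Three stronger readings are tempting, and the documents do not support them:
- *That many women are still using DNG at last contact.* No such figure is given. SAP section 4 expects most women to stop or change regimen, and the censored share depends heavily on the assumed stopping rate.
- *That start dates explain the country differences.* They explain part; real differences in persistence may also exist.
- *That staggered entry distorts the whole table.* For women on DNG from entry in the main block, the loss at or below 48 months comes only from drop-out. Women who switch to DNG later, whom the footnote admits, have less time and can be cut off earlier.

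**Conclusion.** The point holds as a reporting defect in a secondary, descriptive output. Read as duration of use, the shares beyond 48 months are too low whenever any use is censored, and the country tables cannot be compared in those rows. The proportional loss at 60 months, about 37% without drop-out and 58% with the planned 10% a year, rests on the assumed entry pattern and on DNG use from entry. The absolute gap rests on stopping rates that the documents do not give: without drop-out it is about 15 percentage points at 0.25/year and about 2 at 0.8/year. The empty rows in the three countries opened in 2012 need no assumption about stopping; they follow from the calendar for women using DNG from entry or later. The primary hypotheses on anemia, depression and treatment failure are unaffected.

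**What to change.** 1. In B-7.1.1 to B-7.1.12, split each duration row into *stopped* and *ongoing or last known on treatment*.
2. Label the tables as duration observed to last contact.
3. Add a Kaplan-Meier estimate of continuous DNG use from the start of the DNG episode, censored at last contact, drop-out or study end, with 95% confidence intervals and numbers at risk, overall and by country. State that it assumes censoring unrelated to stopping.

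Curves for OAED or the non-approved medications (NAED) are optional. If added, they must handle planned end of treatment separately: SAP section 5.2 keeps completion of a pre-defined course, such as a GnRH agonist, out of treatment failure, and a simple all-cause curve would count it as stopping.

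The cost is a few lines of SAP text and some standard programming. Question 1 of the follow-up questionnaire already records from and to dates and an ongoing box for each medication, so no new data are needed.
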